4 LIST OF ABBREVIATIONS AND DEFINITIONS OF TERMS

Abbreviation	Term
ABNAS	A-B neuropsychological assessment schedule
AE(s)	adverse event(s)
AED	antiepileptic drug
ALT	alanine aminotransferase
AST	aspartate aminotransferase
β-hCG	beta-human chorionic gonadotropin
BP	blood pressure
CBCL	Child Behavior Checklist
CGI	Clinical Global Impression
CGIC	Clinical Global Impression of Change
CGIS	Clinical Global Impression of Severity
CNS	central nervous system
CRAs	Clinical research associates
CRF	case report form
CRO(s)	contract research organization (s)
C _{ss,av}	average steady-state drug concentration
C-SSRS	Columbia-Suicide Severity Rating Scale
CL/F	Clearance
DEA	Drug Enforcement Administration
DMC	Data Monitoring Committee
EAP	extended access program
eGFR	estimated glomerular filtration rate
EIAED	enzyme inducing antiepileptic drug
EMA	European Medicines Agency
EQ-5D-Y	EuroQol 5 Dimensions-Youth
FAS	Full Analysis Set
GTC	Generalized Tonic-Clonic
hCG	human chorionic gonadotropin
HRQL	health-related quality of life
ICF	informed consent form
ICH	International Council for Harmonisation of Technical Requirements for Pharmaceuticals for Human Use
IEC	Independent Ethics Committee

Abbreviation	Term
IGF-1	insulin-like growth factor-1
IP	investigational product
IRB	Institutional Review Board
IxRS	interactive and response system
LGPT	Lafayette Grooved Pegboard Test
LNH	low/normal/high
MedDRA	Medical Dictionary for Regulatory Activities
PD	Pharmacodynamics
PGTC	primary generalized tonic-clonic seizures
PI	principal investigator
PK	Pharmacokinetics
POS	partial-onset seizures
PT	preferred term
QTc	corrected QT interval (time from the beginning of the QRS complex to the end of the T wave, corrected for heart rate)
SAE	serious adverse event
SAP	statistical analysis plan
SMQ	standardized MedDRA queries
SOC	system organ class
TEAE	treatment-emergent adverse event
TEMAV	treatment-emergent markedly abnormal laboratory values
ULN	upper limit of normal
VNS	vagal nerve stimulator
WBC	white blood cell

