 7. Are scheduled or confirmed or both to have epilepsy surgery within 6 months after Visit 1; however, those who have previously documented "failed" epilepsy surgery will be allowed.
 8. Evidence of clinically significant disease (eg, cardiac, respiratory, gastrointestinal, renal disease) that in the opinion of the investigator(s) could affect the subject's safety or interfere with the study assessments.
 9. Evidence of moderate or severe renal insufficiency as defined by estimated glomerular filtration rates (eGFRs) of 31 to <60 mL/min and <30 mL/min, respectively. (revised per Amendment 01)
 10. Evidence of significant active hepatic disease. Stable elevation of liver enzymes, ALT and AST due to concomitant medication(s), will be allowed if they are less than 3 times the upper limit of normal (ULN).
 11. Evidence of significant active hematological disease; white blood cell (WBC) count equal or less than 2500/ μ L (2.50 1E+09/L), or an absolute neutrophil count equal or less than 1000/ μ L (1.00 1E+09/L).
 12. Clinically significant ECG abnormality, including prolonged corrected QT interval (QTc) defined as greater than 450 msec.
 13. Have a progressive central nervous system (CNS) disease, including degenerative CNS diseases and progressive tumors.
 14. Multiple drug allergies or a severe drug reaction to an AED(s), including dermatological (eg, Stevens-Johnson syndrome), hematological, or organ toxicity reactions.

15. Concomitant use of felbamate as an AED for less than 2 years or where the dose has not been stable for at least 8 weeks before Visit 1. They must not have a history of WBC count below equal or less than 2500/ μ L (2.50 1E+09/L), platelets below 100,000, liver function tests (LFTs) above 3 times the ULN, or other indication of hepatic or bone marrow dysfunction while receiving felbamate. If subjects received felbamate in the past, it must have been discontinued 8 weeks before Visit 1 to be eligible for study participation.
16. Concomitant use of vigabatrin: Subjects who took vigabatrin in the past must be off vigabatrin for at least 5 months before Visit 1 and with documentation showing no evidence of a vigabatrin associated clinically significant abnormality in a visual perimetry test.
17. Concomitant use of cannabinoids. (revised per Amendment 01)

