Abnormal ECG (QTc) results, if not otherwise considered part of a clinical symptom that is being reported as an AE, should be considered an AE if the QTc interval is more than 450 ms and there is an increase of more than 60 ms from baseline. Any ECG abnormality that the investigator considers as an AE should be reported as such.

It is the responsibility of the investigator to review the results of the C-SSRS in all subjects and determine if any result constitutes an AE. Medical and scientific judgment should be exercised in deciding whether an isolated suicidality rating scale response should be classified as an AE (see [Section 9.5.1.5.7](#) for a description of the C-SSRS).

All AEs must be followed for 28 days after the subject's last dose, or until resolution, whichever comes 1st. All SAEs must be followed to resolution or, if resolution is unlikely, to stabilization.

Every effort must be made by the investigator to categorize each AE according to its severity and its relationship to the study treatment.

Assessing Severity of Adverse Events

AEs will be graded on a 3-point scale (mild, moderate, severe) and reported in the detail indicated on the CRF. The definitions are as follows:

Mild Discomfort noticed, but no disruption of normal daily activity

Moderate Discomfort sufficient to reduce or affect normal daily activity

Severe Incapacitating, with inability to work or to perform normal daily activity

The criteria for assessing severity are different from those used for seriousness (see Section 9.5.1.5.2 for the definition of an SAE).

Assessing Relationship to Study Treatment

Items to be considered when assessing the relationship of an AE to the study treatment are:

- Temporal relationship of the onset of the event to the initiation of the study treatment
- The course of the event, especially the effect of discontinuation of study treatment or reintroduction of study treatment, as applicable
- Whether the event is known to be associated with the study treatment or with other similar treatments
- The presence of risk factors in the study subject known to increase the occurrence of the event
- The presence of nonstudy, treatment-related factors that are known to be associated with the occurrence of the event

Classification of Causality

The relationship of each AE to the study drug will be recorded on the CRF in response to the following question:

Is there a reasonable possibility that the study drug caused the AE?

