- g: Weight and Height (without shoes) will be measured. Three measurements should be taken at each visit. Each measurement should be recorded as a separate entry on the Vital Sign eCRF.
- h: Only for those subjects who continue into Extension A.
- i: Unused study drug to be retrieved and study drug dispensed only for subjects requiring dose increases at Unscheduled Visits.
- j: Clinical laboratory tests include hematology, blood chemistry including lipid panel, and urinalysis.
- k: Fasting lipid and glucose samples to be taken at baseline and at end of treatment or early discontinuation, with fasting window (interval) between 2 and 4 hours.
- l: Female subjects age 8 years old and above, or of childbearing potential, only. If urine can not be obtained for pregnancy testing after screening, a serum pregnancy test will be performed. (revised per Amendment 01)
- m: Only for subjects aged 6 years and older at the time of consent/assent.
- n: If subject has a normal ECG baseline reading, but during any visit thereafter, the QT is measured as greater than 450 ms, 3 consecutive ECGs separated by 5 to 10 minutes will be performed to confirm the abnormality.
- o: During Unscheduled Visits, ECG or EEG will only be done if the results from the previous visit were deemed clinically significant by the investigator.
- p: EEG will be performed at awake and sleep state for all subjects.
- q: One blood sample (approximately 1 mL) for determination of perampanel plasma concentrations will be collected at any time during each of the specified visits.

Table 4 Schedule of Procedures/Assessments in Study E2007-G000-311: Core Study

Phase	Pre-Treatment	Treatment Phase									Early Discontinuation ^d	Unscheduled
	Screening/Baseline	Titration ^a				Maintenance ^b				Follow-up ^{b,c}		
Visit	1	2	3	4	5	6	7	8	9			
Week	From up to -4 weeks ±3 days to Week 0 (outside of Japan) -4 weeks ±3 days to Week 0 (Japan only) (revised per Amendment 02)	0	2	5	8	11	15	19	23	27		
Procedures/Assessments												

- r: Additional blood (approximately 1 mL/sample) will be drawn at the 1st report (where possible) of a serious adverse event or severe unexpected AE and at its resolution. (revised per Amendment 01)

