9.7.1.8.5 ELECTROCARDIOGRAMS

Descriptive statistics for ECG parameters and changes from baseline will be presented by visit.

Shift tables will present changes from baseline in ECG interpretation (categorized as normal; abnormal, not clinically significant; and abnormal, clinically significant) to end of treatment.

In addition, the number (percentage) of subjects with at least 1 postbaseline abnormal ECG result in QTc Bazett and QTc Fridericia during the treatment period will be summarized. Clinically borderline or abnormal ECG results in QTc Bazett and QTc Fridericia will be categorized as follows:

Absolute QTc interval prolongation:

- QTc interval 430-450 ms
- QTc interval >450 ms
- QTc interval >500 ms

Change from baseline in QTc interval:

- QTc interval increases from baseline 30-60 ms
- QTc interval increases from baseline >60 ms

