- k: Female subjects age 8 years old and above, or of child-bearing potential, only.
- l: Only for subjects aged 6 years and older at the time of consent/assent.
- m: If during any visit the QTc was measured as greater than 450 ms, 3 consecutive ECGs separated by 5 to 10 minutes will be performed to confirm the abnormality.
- n: During the unscheduled visits, ECG or EEG will only be done if the results from the previous visit were deemed clinically significant by the investigator.
- o: EEG will be performed in awake and sleep state in all subjects.
- p: Telephone interviews with the subjects and/or caregiver will be conducted 2 weeks (± 3 days) after Visit 10 through 12, to ensure that subjects are completing their seizure diaries regularly and assess AEs, study drug compliance and concomitant medications, including AEDs. Subjects whose dose was decreased before the scheduled telephone interview will be strongly encouraged to return to the clinic (instead of the scheduled telephone interview) for further consultation with regard to study drug administration. The site will contact IxRS to receive further dispensing instructions. Subjects will then return for their regularly scheduled visits.
- q: ABNAS to assess patient-perceived cognitive effects of AED treatment, measuring 5 aspects of cognitive function: fatigue, memory, concentration, motor speed, and reading, using a 4-point scale.

Statistical Analyses

Statistical analyses will be performed by the sponsor or designee after the study is completed, the database is locked and released, and a snapshot of the database is obtained and released. Analyses for regional submissions may be performed during the course of the study. (revised per Amendment 02) Statistical analyses will be performed using SAS software or other validated statistical software, as required. Details of the statistical analyses will be included in a separate SAP.

Analysis Sets

Safety Analysis Set is the group of subjects who received at least 1 dose of study drug and had at least one postdose safety assessment in Extension A. (revised per Amendment 03)

FAS is the group of subjects who received at least 1 dose of study drug and had at least 1 postdose seizure measurement in Extension A. (revised per Amendment 03)

Efficacy Analyses

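### The Core Study rule for repeat ECGs (Protocol Table 4, note n) is triggered by uncorrected QT above 450 ms, where every other 450 ms rule uses QTc

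*Protocol*

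**What the plan says.** Protocol Section 9.5.2.1, Table 4, note n governs repeat ECGs in the Core Study. If the baseline ECG was normal and at a later visit "the QT is measured as greater than 450 ms", the site takes three ECGs 5 to 10 minutes apart to confirm the finding.

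Protocol Appendix 1, Table 5, note m orders the same three ECGs in Extension A, but its condition is "If during any visit the QTc was measured as greater than 450 ms".

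The other rules with a 450 ms cut-off are:

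- Exclusion 12 (Synopsis and Section 9.3.2): "prolonged corrected QT interval (QTc) defined as greater than 450 msec".
- The adverse-event rule (Section 9.5.1.5.1), which sets two joint conditions for calling an abnormal result an adverse event: "if the QTc interval is more than 450 ms and there is an increase of more than 60 ms from baseline".
- The analysis categories (Protocol Section 9.7.1.8.5 and Appendix 1; Section 5.6.5 of both the Core and Extension SAPs): "QTc interval >450 ms", by Bazett and by Fridericia.

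Protocol Section 4 defines QTc as "corrected QT interval (time from the beginning of the QRS complex to the end of the T wave, corrected for heart rate".

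**The concern.** QT and QTc are different quantities, and they agree only at 60 bpm. Above that rate QTc exceeds QT, so a trigger of 450 ms on QT is laxer than the same number on QTc. A Core tracing with QTc above 450 ms and QT at or below 450 ms would need no repeat under note n. The same tracing in Extension A would need three.

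By Table 4, a child who completes the Core Study has one scheduled on-treatment ECG, at Visit 9 (Week 23). The other planned Core ECGs after baseline are at Early Discontinuation and Follow-up. By Table 5, a child who rolls over has the next scheduled ECG at Visit 12 (Week 52), which is 52 − 23 = 29 weeks later, and dose increases are allowed in between. A prolonged QTc at Visit 9 could therefore go unconfirmed for that time unless the investigator acts on their own judgement.

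**Working it through.** **Text comparison.** I compared every 450 ms ECG rule in the protocol and both SAPs. Note n is the only one that names QT. No text equates QT with QTc, and none gives a reason for an uncorrected trigger in the Core Study. The abbreviation list under Table 4 omits QTc while the one under Table 5 defines it, so a PDF reading error is an unlikely explanation.

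**Size of the gap.** The plan has no figure of its own to reproduce. The inputs are the 450 ms cut-off (from the documents) and heart rate (assumed, since the documents give none for these children). I used 70 to 120 bpm, with 60 bpm as the reference. In the Core SAP (Section 5.6.4, Table 1), the criterion values for a clinically notable heart rate are above 120 and below 50 bpm, so the assumed range is not notable by the plan's own limits.

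With RR = 60 / heart rate, in seconds:

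- Bazett: QTcB = QT / RR^(1/2), so QTcB = 450 ms when QT = 450 × RR^(1/2).
- Fridericia: QTcF = QT / RR^(1/3), so QTcF = 450 ms when QT = 450 × RR^(1/3).

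Example at 100 bpm: RR = 0.600; 450 × 0.600^(1/2) = 348.6 ms; 450 × 0.600^(1/3) = 379.5 ms.

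| Heart rate (bpm) | RR (s) | QT giving QTc 450 ms, Bazett / Fridericia | Width of missed QT range up to 450 ms | QTcB / QTcF when QT = 450 ms |
|---|---|---|---|---|
| 60 | 1.000 | 450.0 / 450.0 | 0 / 0 | 450 / 450 |
| 70 | 0.857 | 416.6 / 427.5 | 33.4 / 22.5 | 486 / 474 |
| 80 | 0.750 | 389.7 / 408.9 | 60.3 / 41.1 | 520 / 495 |
| 90 | 0.667 | 367.4 / 393.1 | 82.6 / 56.9 | 551 / 515 |
| 100 | 0.600 | 348.6 / 379.5 | 101.4 / 70.5 | 581 / 534 |
| 120 | 0.500 | 318.2 / 357.2 | 131.8 / 92.8 | 636 / 567 |

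At 90 bpm or more, note n read literally fires only when QTc is already above 500 ms by both formulas, which is the plan's highest absolute category. Below 60 bpm the order reverses: at 50 bpm a QTc of 450 ms needs a QT of 493.0 (Bazett) or 478.2 ms (Fridericia), so there note n is the stricter rule.

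**The case against.** The strongest reply is that this is a small wording slip. The only abnormality the plan defines at 450 ms is a QTc abnormality, so many sites would read note n that way. The AE rule also requires someone to look at QTc on Core tracings, and it is numeric, not discretionary. Beyond it, "Any ECG abnormality that the investigator considers as an AE should be reported as such", and under Table 4 note o, at Unscheduled Visits "ECG or EEG will only be done if the results from the previous visit were deemed clinically significant by the investigator". Finally, note n has a normal-baseline condition that note m lacks, so changing one word does not make the two notes identical, and QTc without a named formula still leaves two possible triggers.

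Much of this stands as a limit on the consequences. It does not remove the inconsistency. The AE rule needs a rise of more than 60 ms as well as QTc above 450 ms, and it orders no repeat. The other two safeguards depend on the investigator, and neither is a repeat at the same visit. If some sites read QT as QTc and others do not, practice will differ between sites. The baseline condition is a separate difference. The missing formula is a fair point, but it applies equally to note m. The heart rates are illustrative: the table shows how the formulas behave, not how often such tracings will occur.

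**Conclusion.** The concern holds. As written, note n is the only 450 ms ECG rule in the plan that uses the uncorrected interval, and above 60 bpm it leaves some prolonged QTc tracings without the confirmation that Extension A would require. At an assumed 80 to 100 bpm, the missed QT range is about 60 to 101 ms wide by Bazett and 41 to 70 ms by Fridericia. How many children fall in it cannot be estimated from the documents. That it is a drafting slip is an inference, from the matching action and cut-off in note m and the absence of any rationale.

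The effect is confined to confirming a prolonged QTc at the site. No endpoint definition or dosing rule uses the repeats. The QTc outlier tables count children with at least one abnormal post-baseline result, so the initial tracing can count without them. This is worth correcting because sites act on the rule, but it does not threaten the study's analyses.

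**What to change.** In Protocol Table 4, note n, replace QT with QTc, so that the trigger is a QTc above 450 ms as in Table 5, note m. Naming the correction formula in both notes would be a useful addition, since at 100 bpm the two formulas place the trigger 379.5 − 348.6 = 30.9 ms of QT apart. The one-word change stands without it.

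The cost is one word in one table note, made by administrative change or amendment under Protocol Section 11.1, plus some additional repeat ECGs of a kind already planned. Their number depends on heart rate and formula and cannot be computed from the documents. At 100 bpm the trigger would fall from a QT of 450 ms to about 349 ms (Bazett) or 380 ms (Fridericia).
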